7.7. Other Secondary Efficacy Analyses - Time to Event Endpoints

7.7.1. Summary Measures

The hazard ratio of Arm B (combination) and Arm A (control).

7.7.2. Population of Interest

The secondary efficacy analyses will be based on the modified Intent-To-Treat population, unless otherwise specified.

7.7.3. Strategy for Intercurrent (Post-Randomization) Events

Subjects without an event will be considered censored at the last observed timepoint.

7.7.4. Subgroup, Supportive and Sensitivity Analyses

There are no planned subgroup, supportive or sensitivity analyses for other secondary endpoints.

7.7.5. Statistical Methodology Specification for Time to Event Endpoints

| |
|--|
| Endpoints |
| 
 Time to first severe flare (as measured by the modified SLE Flare Index) [T12.33, T22.22, F12.12,F22.06] |

- Time to first flare (as measured by the modified SLE Flare Index) [T12.34, T22.23,F12.09,F22.07]
- Time to disease control sustained to Week 104, defined as SLEDAI-2K score ≤ 2 (PI), achieved without immunosuppressants and with corticosteroids at a prednisone equivalent dose of ≤ 5 mg/day.[T22.24,F22.09].
- Time to clinical remission sustained to Week 104, defined as Clinical SLEDAI-2K score=0 (PI) (Section 15.6.3), achieved without immunosuppressants and with corticosteroids at a prednisone equivalent dose of 0 mg/day [T22.33].

Derivation

Flare Endpoints

| Subject | Time to defined as: | Censored |
|--|---|----------|
| Flare | Date of 1 st flare – trt start date +1 | No = 0 |
| TF before or without flare | Date of 1 st TF – trt start date +1 | No = 0 |
| Subjects without a Flare or TF who have an intercurrent event: | | |
| Withdraw | Date of last Flare assessment prior to intercurrent event – trt start date +1 | Yes =1 |
| Lost to Follow-up | | |
| Die | Date of Death – trt start date +1 | Yes =1 |
| For Year 1 reporting: | | |
| Subject completes Week 52 | Date of Week 52 visit – trt start date +1 | Yes =1 |
| For Year 2 reporting: | | |
| Subject completes Week 104 | Date of Week 104 visit – trt start date +1 | Yes =1 |

- The flare criteria will be programmed from the SLEDAI-2K irrespective of data recorded on the SFI form
- Flares recorded as severe on the SFI form will be downgraded to not severe in the programmed endpoint if the only cause of the severe flare was SLEDAI-2K>12
- Only post baseline flares will be included in the analysis (Flares on Day 1 will not be considered)
- Treatment failure is considered as a severe flare.
- Subjects who do not have a flare assessment post baseline will be censored at Day 1 and hence reported as 'time to' defined as 1 and censor =Yes = 1

Time to Response Endpoints

| Subject | Time to defined as: | Censored |
|---------------------------------------|--|----------|
| Sustained response | Date of 1 st sustained response – trt start date +1 | No = 0 |
| | | |
| Subjects without a sustained response | | |

| | | |
|--|--|--------|
| Withdraw | Date of last visit prior to intercurrent event – trt start date +1 | Yes =1 |
| Lost to Follow-up | | |
| Treatment Failure | | |
| Die | Date of Death – trt start date +1 | Yes =1 |
| For Year 1 reporting: | | |
| Subject completes Week 52 without treatment failure | Date of Week 52 visit – trt start date +1 | Yes =1 |
| For Year 2 reporting: | | |
| Subject completes Week 104 without treatment failure | Date of Week 104 visit – trt start date +1 | Yes =1 |

Further detail is provided in Section [15.6.7](#).

Model Specification

A Cox proportional hazards model controlling for treatment group, baseline SLEDAI-2K score (≤ 9 vs. ≥ 10), baseline immunosuppressant use (use vs. non-use), and baseline corticosteroid dose (prednisone equivalent ≤ 10 mg/day vs. >10 mg/day) will be used to evaluate time to event endpoints.

Ties will be managed using Efron’s approximation.

Model Checking & Diagnostics

Overall model Goodness of fit tests using the -2 Log Likelihood, Akaike’s Information Criterion (AIC), and Schwarz Bayesian criterion (SBC) tests will be performed. The AIC and SBC statistics offer two different ways of adjusting the -2 log likelihood statistic for the number of terms in the model and the number of observations used. Lower values in these statistics represent a more desirable model. These tests will aid in the assessment of model fit but the final decision regarding goodness of fit will be based on statistician review. If the model fit is considered inadequate additional analysis will be conducted.

Model Results Presentation

A table for each endpoint [as above] will present:

- The number and percentage of subjects with an event and the median, 25th percentile, and 75th percentile of days to event by treatment group,
- the hazard ratio and 95% confidence interval (CI) for the comparison of Arm B vs Arm A; and Arm B vs Arm C.
- the p-value for the hazard ratio for Arm B vs Arm A.
- the median, 25th percentile, and 75th percentile of days, min and max for the study day of 1st event

A Kaplan-Meier plot of time to event for each endpoint will be displayed by treatment group.

Subgroup Analyses

Subgroup analyses will not be conducted for secondary endpoints.

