7.1. Primary Efficacy Analyses

7.1.1. Endpoint / Variables

The protocol defined primary endpoint is the proportion of participants with a state of disease control defined as a SLEDAI-2K score ≤ 2 (IBA), achieved without immunosuppressants and with corticosteroids at a prednisone equivalent dose of ≤ 5 mg/day at Week 52 (Protocol Section 4).

The protocol Section 10.4.1 Efficacy analysis then clarifies that:

For participants who withdraw prematurely from study treatment and for who subsequent collection of data is not possible, it will be assumed for the primary analysis that they are treatment failures. A dropout/treatment failure = non-responder (DO/TF=NR) analysis will be used .

Hence when adopting the ICH Estimands and Sensitivity Analysis in Clinical Trials E9 R1 addendum terminology, this endpoint is defined as:

| Disease Control |
|--|
| 
Responder:
 
 • SLEDAI-2K score ≤ 2 (IBA); and • Not a TF at the current or any prior visit (TF includes consideration of corticosteroids and immunosuppressants); and • Did not withdraw from the study prior to the visit 
Non-Responder:
 
 • SLEDAI-2K score > 2 (IBA); or • TF at the current or any prior visit (TF includes consideration of corticosteroids and immunosuppressants); or • Withdrew from the study prior to visit (which includes study withdrawal, lost to follow-up and death) |
| 
The derivation of SLEDAI-2K score is provided in Section 15.6.3, treatment failures are defined in Section 15.6.15. and withdrawal from the study prior to Week 52 in Section 5.9.
 |
| 
Note: Discontinuation of study investigational product (belimumab or rituximab) is NOT a component of this endpoint, subjects who discontinue investigational product will only be non-responders if they also meet one of the criteria above.
 |

Note this clarification of notation does not change the protocol-specified primary analysis.

The analysis of the primary endpoint of Arm A vs Arm B will use data from treatment Arms A, and B only.

An exploratory analysis of the relative performance of Arm B vs. Arm C will also be conducted, using data from Arms B and C only.

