7.1.4. Strategy for Intercurrent (Post-Randomization) Events

There are 5 potential types of intercurrent events considered for this study:

- Treatment Failure
- Study Withdrawal
- Lost to Follow-up
- Death
- Investigational Product (IP) Discontinuation .

Whilst study withdrawal and lost to follow-up (LTFU) are not true intercurrent events per ICH Estimands and Sensitivity Analysis in Clinical Trials E9 R1 addendum terminology; they are included in the reporting here to allow for backward compatibility to the study Protocol (see Section [7.1.1](#)).

Four intercurrent event strategies are employed:

- Hybrid strategy considers all data while the subject is continuing in the study irrespective of IP discontinuation. Treatment failure and study withdrawal (including LTFU and death) are components of the endpoint definition. Subjects who discontinue investigational product (belimumab) are encouraged to continue in the study.
- Composite strategy considers data collected only while the subject is continuing to receive study treatment. Treatment failure and study withdrawal (including LTFU and death), and IP discontinuation are components of the endpoint definition.
- Hybrid on treatment strategy considers data collected only while the subject is receiving study treatment. Treatment failure and study withdrawal (including LTFU and death), are components of the endpoint definition. IP discontinuation are excluded (unless already experienced treatment failure).
- Treatment Policy strategy considers all data while the subject is continuing in the study irrespective of IP discontinuation or Treatment Failure. Study withdrawal (including LTFU and death), are components of the endpoint definition

The main estimand of this endpoint, is a Hybrid strategy, subjects who discontinue investigational product will continue in the study, assessments after treatment discontinuation will be included in the main estimand. Subjects who are a treatment failure or withdraw from the study will be a non-responder for this estimand.

An analysis of 3 supportive estimands will also be conducted using the alternative intercurrent event strategies, namely:

- Composite,
This will include IP discontinuation as an intercurrent event resulting in the subject being a non-responder.
- Hybrid On treatment,
This will only include subjects whilst they are on treatment, or if they have met the definition of a non-responder prior to discontinuing treatment.
- Treatment Policy,

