| 
Clinical Remission Sustained For At Least 24 Weeks
 
Sustained response will be reported for all weeks post Week 52 (Year 2), and at any timepoint (i.e. any subjects who had a sustained response at any time during Year 2). Statistical analysis will only be conducted at Week 104 and at ‘any timepoint’.
 
A subject has a sustained remission at a visit if all of the following criteria are met:
 
 1 In clinical remission at the visit 2 In clinical remission at the first visit at least 24 study weeks prior, or if clinical remission cannot be assessed at that visit, then in clinical remission at the visit prior. 3 In clinical remission for all assessed visits between (1) and (2). – Note assessments can be missing. 
Note: 24 weeks refers to the difference in visit ‘labels’ not calendar weeks between visits.
 |

[figure not shown]
| |
|--|
| Time to Clinical Remission Sustained to Week 104 |
| The first visit of sustained clinical remission is defined as the 1 st visit that the subject is a clinical remission responder and all subsequent visits up to and including Week 104 the subjects is also a clinical remission responder. Missing assessments are not considered (the rules for sustained response for at least 24 weeks as defined above are also applied here). |
| Time to clinical remission sustained to Week 104 = 1 st visit of sustained clinical remission - treatment start date (Day 1) +1 |
| Duration of Clinical Remission |
| The duration of clinical remission is defined as the longest period between 2 visits that the subject is a clinical remission responder at all visits. Missing assessments are not considered Duration of clinical remission = longest period where 1 st visit of clinical remission – last visit of clinical remission + 1 |

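### Time to sustained response (Tables 22.11 and 22.21) censors participants who can no longer respond, so the hazard ratio moves toward the arm with more or earlier failures

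*SAP*

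**What the plan says.** RAP Section 7.7.5 gives the derivation for the two time-to-response endpoints. A participant without sustained response who withdraws, is lost to follow-up or has a treatment failure is censored at the "Date of last visit prior to intercurrent event". A death is censored on its date. The remaining non-achievers, described as "Subject completes Week 104 without treatment failure", are censored at their Week 104 visit. Section 7.7.3 states the general rule: "Subjects without an event will be considered censored at the last observed timepoint".

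The event depends on what happens later. Section 15.6.5 dates it at the first remission visit for which, at "all subsequent visits up to and including Week 104 the subjects is also a clinical remission responder"; Section 15.6.4 does the same for disease control. A responder must also be "Not a TF at the current or any prior visit" (Section 7.1.1; likewise 7.2.1) and must not have withdrawn, been lost or died.

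The analysis is a Cox model with Efron ties, giving a hazard ratio, confidence interval and p-value. The tables also print the number and percentage with an event and the median, 25th and "75th percentile of days to event by treatment group". Section 7.7.4 adds: "There are no planned subgroup, supportive or sensitivity analyses for other secondary endpoints".

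The second RAP addendum (Section 2.1.4) keeps both tables, as 22.11 (old 22.33) and 22.21 (old 22.24), and labels them Hybrid. Section 7.1.4 defines that strategy so: "Treatment failure and study withdrawal (including LTFU and death) are components of the endpoint definition".

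**The concern.** Censoring is meant for participants whose later outcome is unknown. Here it is known: after a treatment failure, withdrawal, loss or death, a response held to Week 104 is impossible. (Someone who leaves but has a visit within 28 days of Week 104 does not count as withdrawn under Section 5.9 and is not meant here.) These participants drop out of the risk set while completers without response stay in it.

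What the Cox model then estimates is a cause-specific hazard ratio. It does not describe the chance or timing of sustained response, and the RAP does not present it as cause-specific. A Kaplan-Meier quartile built this way treats failed participants as if they could still respond. The derivation also does not deliver what the Hybrid label says, which is that failure and withdrawal count as non-response.

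At stake are the hazard ratio, p-value and quartiles in these two tables. The comparison of Arm B with Arm C is exposed by design, because prescribed re-start belimumab, and any immunosuppressant after Week 4, are failures only in Arms A and B (Sections 5.10 and 15.6.15.1).

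**Working it through.** **Inputs from the documents.** Arm sizes are 70 (A) and 140 (B), from Protocol Section 10.2. The stated power of at least 98% for the primary endpoint (10% vs 35%) reproduces at 98.9% by normal approximation and 99.0% by exact enumeration of the likelihood ratio test. The plan gives no event count, hazard ratio or power for the two time-to-response endpoints, so that figure only anchors the arm sizes. Visits are the investigator SLEDAI-2K visits, Weeks 4 to 104, from the Schedule of Activities.

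**Assumed.** Response proportions, failure proportions and their timing. Unless stated otherwise, failure shares are of non-responders.

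**Step 1: last possible event.** A run of at least 24 weeks ending at Week 104 must start by Week 104 − 24 = Week 80. Failures after that do not affect the result; earlier ones can.

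**Step 2: limiting case by hand.** Suppose every failure precedes every response. With true response r and failure share f among non-responders, the fraction still at risk is 1 − f(1 − r), and the Kaplan-Meier estimate under the RAP rule is K = r / [1 − f(1 − r)]. The hazard ratio (B vs A) is about ln(1 − K_B) / ln(1 − K_A). If failures stay at risk, K = r.

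| True response A / B | Failures A / B | K_A | K_B | HR, RAP rule | HR, fixed |
|---|---|---|---|---|---|
| 20% / 20% | 60% / 30% | 0.20/0.52 = 0.385 | 0.20/0.76 = 0.263 | 0.305/0.486 = 0.63 | 1.00 |
| 20% / 20% | 60% / 50% | 0.20/0.52 = 0.385 | 0.20/0.60 = 0.333 | 0.405/0.486 = 0.84 | 1.00 |
| 20% / 20% | 45% / 45% | 0.20/0.64 = 0.313 | 0.313 | 1.00 | 1.00 |
| 10% / 20% | 60% / 30% | 0.10/0.46 = 0.217 | 0.263 | 0.305/0.245 = 1.25 | 0.223/0.105 = 2.12 |
| 10% / 15% | 60% / 30% | 0.217 | 0.15/0.745 = 0.201 | 0.225/0.245 = 0.92 | 0.163/0.105 = 1.54 |

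**Step 3: less extreme timing, by simulation.** Responses start over Weeks 8-80 or 28-80. Failures come just after Week 26 or over Weeks 26-52; the last column spreads them over Weeks 4-104. The model is Cox with Efron ties, treatment only, 20,000 per arm.

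| True response, failures (A / B) | HR, failures by Week 52 | HR, Weeks 4-104 | HR, fixed |
|---|---|---|---|
| 20/20%, 60/30% | 0.63-0.76 | 0.82-0.86 | 1.00 |
| 20/20%, 60/50% | 0.84-0.90 | about 0.95 | 1.00 |
| 20/20%, 45/45% | 0.99-1.00 | about 1.00 | 1.00 |
| 10/20%, 60/30% | 1.24-1.57 | 1.75-1.85 | 2.11 |
| 10/15%, 60/30% | 0.92-1.15 | not reported | 1.54 |

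In the last row the ratio falls below 1 only if every response starts after Week 26 and every failure comes just after Week 26.

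**Step 4: direction, timing and a null check.** In a separate simulation, failure shares were of all participants and true response was 20% in both arms. Failures of 30% (A) and 60% (B) gave 1.27, so the shift reverses with the imbalance. Failures of 50% in both arms, at Weeks 4-40 in A and Weeks 52-104 in B, gave 0.52, against 1.00 when kept at risk. Failures only after Week 88 gave no shift.

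**Step 5: planned size.** At 70 vs 140 with failures 60% vs 30%:
- True 20% vs 20%: p<0.05 in favour of A in 12-30% of trials instead of 2-3%. With failures over Weeks 4-104 it is no more than about 10%.
- True 10% vs 20%: p<0.05 in favour of B in 5-14% instead of 39-41%. With failures over Weeks 4-104 it is 21-26% instead of 41-43%.

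**Step 6: quartiles.** With 20% response and 45% failures in each arm, the Kaplan-Meier estimate reaches 27-31%. A 25th percentile at Week 72-80 would be printed although fewer than 25% respond. With failures over Weeks 4-104 the estimate is about 24-25%, at the margin.

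**The case against.** The case against accepts the censoring mechanics and contests the weight.

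- **The true percentage is in the same tables.** Section 7.7.5 prints the number and percentage with an event, with failures as non-events. That stands and limits the harm, but the hazard ratio, p-value and quartiles beside it could contradict it.
- **Remission has a sound companion.** Table 22.10 reports sustained remission under Hybrid, with statistical analysis at Week 104. That stands for remission. The disease control tables (22.12-22.13, 22.18-22.19) report response at a visit, so Table 22.21 has no such partner.
- **The quartile method is not stated.** Section 7.7.5 does not say that the quartiles come from Kaplan-Meier, and the second addendum keeps no time-to-response figure. The quartile point is therefore conditional on that method.
- **Early failures drive the larger figures.** True. Spreading them over Weeks 4-104 roughly halves the shift or better, but does not remove it.
- **Censoring is specified, and a cause-specific hazard ratio is legitimate.** It can be, but it is not labelled as such, the event is defined by the future course to Week 104, and the Hybrid label says otherwise.
- **Low decision weight.** The endpoints carry no multiplicity control, and power is modest even after correction. If Arm A fails more, which is an inference, the error works against the combination. This limits the priority but does not make the estimate right.

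**Conclusion.** The concern holds, and the rule should be changed. It takes participants known to be non-responders out of the risk set, and the hazard ratio moves toward the arm with more or earlier failures. For a twofold difference in failures (60% vs 30% of non-responders), an equal true response reads as 0.63-0.86, and a true ratio of about 2.1 reads as 1.24-1.85. A smaller difference (60% vs 50%) gives 0.84-0.95. Matched patterns leave the ratio essentially unchanged.

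The direction follows from the definitions. The size rests entirely on assumed failure shares and timing. A false claim of benefit for the combination would need more or earlier failures in Arm B; the more likely risk is that a real difference is masked. The primary and major secondary analyses are not touched.

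**What to change.** For Tables 22.11 and 22.21, replace the withdrawal, loss to follow-up, treatment failure and death rows of the Section 7.7.5 time-to-response derivation with: time = Day 729 (the Week 104 target in Section 15.3.1), censored = Yes. These participants then stay in the risk set as never having responded. Because no event can start after Week 80, any common later censoring time gives the same Cox result.

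Cumulative incidence with these events as competing risks, and a Fine-Gray model, is an acceptable alternative. The flare endpoints are not part of this change.

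The cost is four rows of one derivation table and two tables to re-program. Since it comes after the first database lock and primary analysis, record it as a post-lock change with a written justification in the end-of-study report, and keep the RAP version as a supplementary table.

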During the 52-week double-blind portion of the study, participants in Arms A and B who cannot tolerate discontinuation of immunosuppressants or taper of corticosteroids or, in the opinion of the investigator, require added therapy, will be considered treatment failures for the efficacy endpoints. Blinding to the treatment assignments in Arms A and B will be maintained. At the investigator's discretion, these participants may continue treatment with belimumab, and/or be treated with additional SLE therapies as necessary, including corticosteroids and/or immunosuppressants. Participants in Arm C who are unable to tolerate the corticosteroid taper or, in the opinion of the investigator, require increased doses of their baseline immunosuppressants or addition of a new immunosuppressant will be considered treatment failures for the efficacy endpoints.

Participants in Arms A and B will enter into the 52-week treatment-free, observational phase of the study after completing Week 52 (Weeks 53 through 104). "Treatment-free" refers to no active treatment with study treatment (i.e., belimumab and/or rituximab). Participants in Arm C will continue to receive belimumab SC and their stable immunosuppressants during Weeks 53 through 104. For participants in all three treatment arms, treatment with anti-malarials, NSAIDs, and/or corticosteroids with a prednisone equivalent dose of ≤5 mg/day will be allowed in Weeks 53 to 104.

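### The fit statistics named for the Cox models cannot examine proportional hazards; the gap shows most in the exploratory two-year comparison of Arm B with Arm C

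*SAP*

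**What the plan says.** SAP section 7.7.5 specifies "A Cox proportional hazards model controlling for treatment group" and three baseline factors for four endpoints: time to first severe flare, time to first flare, and time to disease control and to clinical remission sustained to Week 104. Under model checking it lists "Overall model Goodness of fit tests using the -2 Log Likelihood", together with AIC and SBC, and says of them that "Lower values in these statistics represent a more desirable model". They are an aid only: "the final decision regarding goodness of fit will be based on statistician review". The consequence of a poor fit is equally open: "If the model fit is considered inadequate additional analysis will be conducted".

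Each table reports "the hazard ratio and 95% confidence interval (CI) for the comparison of Arm B vs Arm A; and Arm B vs Arm C", but only "the p-value for the hazard ratio for Arm B vs Arm A". Section 7.7.4 plans no sensitivity analyses for these endpoints. In the end-of-study SAP addendum (section 2.1.4), Tables 22.24 to 22.26 cover flares over Years 1 and 2 combined.

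On the treatment contrast, protocol sections 1 and 5.1 give belimumab through Week 51 in Arms A and B and through Week 103 in Arm C: "Participants in Arm C will continue to receive belimumab SC and their stable immunosuppressants during Weeks 53 through 104". SAP sections 5.10 and 15.6.15.1 make belimumab after Week 52 a treatment failure in A and B but not in C. Section 7.7.5 counts treatment failure as a flare event; Table 22.25 in the addendum is the exception.

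**The concern.** A single hazard ratio summarises a comparison well only if the ratio is roughly constant over follow-up. The statistics listed do not address that. They are relative measures: a value of AIC for one Cox model means nothing until it is set against the value for another, and no second model is named. Elsewhere the SAP ties diagnostics to assumptions; the ANCOVA sections (7.8.5, 7.9.6) name checks of normality and of homogeneous variance. The Cox section has no equivalent for its own central assumption.

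For B versus C the design gives a concrete reason to expect a change at Week 52. From then on one arm is off belimumab and the other is on it. In Tables 22.24 and 22.26 the definition of an event also widens at that point in one arm only. A benefit in Year 1 and a rebound in Year 2 could then average to a two-year ratio near 1. A reader of that one figure would conclude that nothing happened, when the off-treatment period is much of what Year 2 is there to describe.

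**Working it through.** **The plan's own figure.** No power, event count or sample size is stated for any Cox endpoint. The only related figure is in protocol section 10.2: at least 98% power for the binary Week 52 endpoint, with 70 versus 140 participants and 10% versus 35% response. Pooled rate = (7 + 49)/210 = 0.267. SE under the null = sqrt(0.267 × 0.733 × (1/70 + 1/140)) = 0.0647. SE under the alternative = sqrt(0.09/70 + 0.2275/140) = 0.0540. z = (0.25 − 1.96 × 0.0647)/0.0540 = 2.28, giving 98.9%. An exact likelihood-ratio enumeration gives 99.0%. The figure reproduces but says nothing about the Cox models.

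**Inputs from the documents.** Arm B target 140 and Arm C target 70 (protocol 10.2). 29 Arm C participants fall outside the MITT population (SAP section 4), leaving 70 − 29 = 41. Dropout 10% to 15% (protocol Appendix 13), taken as 12.5%. Two-sided alpha 0.05.

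**Assumptions, not in the documents.** Arm C 52-week event probability p = 15%, 30% or 50%, so the yearly hazard is −ln(1 − p) = 0.163, 0.357 or 0.693. The B:C hazard ratio is 0.60 in Year 1 and 1.67 in Year 2. Baseline covariates are omitted.

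**Method.** 1000 simulated trials per scenario, censored at Week 104. The single-ratio Cox model is compared with one that allows separate ratios before and after Week 52. The period test is 2 × (log likelihood of split model − log likelihood of single model), on 1 df. AIC = −2 log likelihood + 2k.

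**Results, 140 versus 41.**

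| Arm C 52-week event probability | 15% | 30% | 50% |
|---|---|---|---|
| Median single two-year hazard ratio | 1.08 | 1.02 | 0.91 |
| Period test detects the reversal | 28% | 52% | 62% |
| Mean −2 log likelihood, hazards reversed | 500 | 882 | 1215 |
| Mean −2 log likelihood, hazard ratio 1 throughout | 468 | 842 | 1192 |
| AIC prefers the split model, if it is fitted | 49% | 72% | 81% |

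The single ratio is significant in 5% to 8% of trials, while separate fits recover about 0.6 and 1.6 to 1.7. The −2 log likelihood follows the number of events and has no reference value, so it does not flag the reversal. AIC can do so only against a time-varying model, which the SAP does not specify.

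**Other settings.**
- A separate simulation used a 35% yearly event rate, 12% yearly dropout, 1500 trials and 140 versus 41 to 70. Ratios of 0.6 then 1.4 to 1.5 give a single ratio of 0.89 to 0.93; the split gives about 0.60 and 1.43 to 1.51. A Schoenfeld-type test flags 30% to 42% of trials.
- At 140 versus 70 with 0.60 then 1.67, detection rises to 66% (p = 30%) and 81% (p = 50%).
- B versus A, 140 versus 70, assumed ratio 0.5 in Year 1 fading to 1.0 in Year 2: the single ratio is 0.70 (p = 30%) or 0.68 (p = 50%). Waning alone blends the two periods and does not reverse the direction.

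**Hand check of the averaging.** At 140 versus 70, p = 30%, 0.60 then 1.67, mean events are 46.7 in Year 1 and 59.2 in Year 2. Weighting by events, (46.7 × ln 0.60 + 59.2 × ln 1.67)/105.9 = (−23.9 + 30.4)/105.9 = 0.061, a ratio of 1.06. The simulated median is 1.01.

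**The case against.** The strongest reply is that little hangs on this. B versus A is the stated summary measure (SAP 7.7.1) and the only comparison with a p-value, and there both arms stop belimumab at the same time. Arm C is a qualitative reference; protocol section 10.2 plans no inferential tests against it. No primary or major secondary endpoint uses a Cox model. All of this stands, and it sets the priority.

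A second reply is that the plan is not blind to poor fit. A reader might infer that the fallback analysis can never be triggered. The documents do not support that: the final decision is a statistician's, and the end-of-study addendum (section 2.1.5) keeps two-year Kaplan-Meier figures for first severe flare and first flare, where crossing curves would be visible. What remains is narrower. No criterion links a plot to any action, the additional analysis is unspecified, and the addendum lists no curve for Table 22.25 or for the two sustained-response tables (22.11 and 22.21).

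Third, flares already have a Year 1 analysis (T12.33, T12.34), so a Year 1 benefit would not vanish from the report. That is correct; only the later period lacks an estimate.

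Fourth, simulating a reversal and then finding that it averages out does not show that a reversal is likely. That is also correct. The simulation shows what the named statistics would miss, and nothing about how probable it is.

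**Conclusion.** The concern holds as a specification gap. The statistics in section 7.7.5 are described as goodness-of-fit tests but are relative measures without a comparator, and no proportional-hazards criterion is written anywhere for these endpoints. With 140 versus 41 and assumed ratios of 0.6 then 1.67, the single two-year ratio is 0.91 to 1.08; with a Year 2 ratio of 1.4 to 1.5 it is 0.89 to 0.93. Tests detect the change in about 28% to 62% of such trials, so reporting by period should not wait for a significant test. The event rates and period ratios are assumptions.

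Two stronger readings should be resisted. One is that the Week 52 stop undermines the B versus A hazard ratio. It separates B from C only; in B versus A another cause is needed, such as waning of the single rituximab cycle. The other is that treatment failure rules make every flare table non-proportional. The steroid rule after Week 26 applies alike in all arms (SAP 15.6.15.1), so by itself it only moves the baseline hazard, and Table 22.25 does not count treatment failures as flares. The rule that does differ by arm at Week 52 concerns belimumab, and it bears on the comparisons with Arm C.

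These are other secondary endpoints outside the multiplicity procedure (SAP 5.6). Priority is low to moderate.

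**What to change.** In SAP section 7.7.5, replace the -2 log likelihood, AIC and SBC text with a named proportional-hazards check, either a Schoenfeld-residual test or a treatment-by-period term split at Week 52, and add log(-log) plots.

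In the Year 1 and 2 flare tables, whatever the test shows, add Kaplan-Meier event-free proportions at Weeks 52 and 104 by arm. Beside the existing Year 1 hazard ratio, give a Weeks 53-104 hazard ratio labelled as descriptive and conditional on being event-free at Week 52.

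The cost is a paragraph of SAP wording, one extra model term and two event-free proportions per arm in each table. There are two drawbacks. Intervals within each period will be wider, markedly so for Arm C with about 41 participants. And the Year 2 estimate is no longer a fully randomised comparison, because treatment may have affected who reached Week 52 without an event. The event-free proportions do not carry that conditioning and should be read first.
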